6.1 General Considerations

The statistical analysis is focused on assessing performance of the Eversense® 180 CGM System in measuring glucose concentration under various clinical situations (day-to-day normal use, hypoglycemia and hyperglycemia). The accuracy of Eversense® 180 CGM System is assessed by comparing with measurements from:

1. Capillary blood glucose concentration from Self-Monitoring Blood Glucose Meter
2. Yellow Springs Instrument (YSI model 2300 blood glucose analyzer) reference glucose test

All statistical analysis will be conducted using SAS version 9.3 or later (SAS Institute Inc., Cary, NC) or other widely-accepted statistical or graphical software as required.

6.1.1 Descriptive Statistics

Participants' demographic and baseline data and their outcome data collected during the course of this study are summarized as descriptively in Tables, Figures and Listings.

Continuous data will be summarized as means, standard deviations, medians, minimums, maximums, and number of evaluable observations. Categorical variables will be summarized as frequency counts and percentages. Confidence intervals may be presented where appropriate.

6.1.2 Study Day

Day 0 (Visit 2 in the study schedule) is the date of insertion of the Sensor. Day in study will be calculated as Study Day = Visit Date – Date of insertion of the Sensor.

Duration in study will be based on last study contact date, which is the latest date of all follow-up visits or assessments, adverse event onset or resolution, or study exit including date of death. It will be calculated as Duration Days = Study Exit – Date of insertion of the Sensor.

6.1.3 Visit Windows

Unless otherwise specified, visit based assessments will be analyzed for each analysis time point according to the nominal visit entered in the Case Report Form (CRF) regardless of if it is out of window.

Statistical Analysis Plan		Page 14 of 28
Sponsor Senseonics, Incorporated	Study PROMISE Study: A Prospective, Multicenter Evaluation of Accuracy and Safety of an Implantable Continuous Glucose Sensor Lasting up to 180 Days	Version 3.0

6.2 Analysis Populations

The following analysis populations are defined for analysis:

1. Per-protocol effectiveness analysis population: This is based on laboratory reference values which are equilibrated with capillary blood glucose values¹, obtained at 15 minutes intervals with matching CGM pairs from measurements, and which are free from protocol deviations, which include:
 - a. Protocol deviations that were not identified at intake (e.g. hematocrit out of window, visit out of window, recent use of tetracycline/sorbitol/mannitol, DKA or Severe hypoglycemia during the past 30 days)
 - b. Flagged reference measurement as indicated in source documentation (e.g., expired membrane, expired calibration, dilute sample)
2. Evaluable analysis population: This is based on data from participants with a minimum of three paired glucose readings since a smaller number of data points from a subject would not be considered representative of intended clinical use. A measurement from the reference test is paired with a reading from the Sensor that took place within a 5-minute period after sample acquisition.
3. Safety analysis population: This is based on data from participants who have undergone the Sensor insertion procedure at day 90 and day 180 visits.

The Per-protocol effectiveness analysis population will be considered the primary analysis set for effectiveness evaluations for the primary sensor configuration described in G180235. The Safety analysis population will be considered the primary analysis set for safety evaluations. Analysis of additional populations will be considered supportive in nature, in particular for the SBA sensor configuration, as described in G180235 S006.

¹ Liu D, et al, "Aterial, arterialized venous, venous and capillary blood glucose measurements in normal man during hyperinsulinaemic euglycaemia and hypoglycaemia", Diabetologia, 1992, 35:287-290.

Statistical Analysis Plan		Page 15 of 28
Sponsor Senseonics, Incorporated	Study PROMISE Study: A Prospective, Multicenter Evaluation of Accuracy and Safety of an Implantable Continuous Glucose Sensor Lasting up to 180 Days	Version 3.0

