11.1.5 EVALUABLE DATA FOR ANALYSIS

All data will be evaluable for the study safety and effectiveness analysis.

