11.1.6 ANALYSIS POPULATION

Effectiveness Analysis population: The effectiveness analysis and exploratory effectiveness endpoints will be based on all data from all subjects in this investigation with at least one paired glucose reading (one Sensor with one reference glucose). The Eversense® 180 CGM System and reference readings are compared by pairing each reference reading with the first Sensor reading that occurred up to 5 minutes after sample acquisition.

Safety Analysis Population: Safety analysis will be based on all subjects that undergo the sensor insertion in this investigation.

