11.3 EFFECTIVENESS ENDPOINTS

11.3.1 SUMMARY

The effectiveness measure will be the mean absolute relative difference (MARD), calculated for all paired Sensor and reference measurements through 180 days post-insertion.

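### SAP 6.2 restricts the primary accuracy set, while the protocol and SAP 6.6.2 use all pairs, so the documents define two headline MARDs, and the SAP's reference "equilibration" has no stated rule

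*SAP*

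**What the plan says.** Protocol Section 11 is consistent on the analysis set. Section 11.1.5 reads: "All data will be evaluable for the study safety and effectiveness analysis". Section 11.1.6 has the effectiveness analysis "based on all data from all subjects in this investigation with at least one paired glucose reading". Section 11.3.1 has MARD "calculated for all paired Sensor and reference measurements through 180 days post-insertion", and 11.3.2.1 divides by the total number of pairs. Nothing there mentions equilibration, thinning or a per-protocol set.

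SAP 6.2 says, for the primary sensor configuration: "The Per-protocol effectiveness analysis population will be considered the primary analysis set for effectiveness evaluations". That set carries three restrictions:

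- reference values are "laboratory reference values which are equilibrated with capillary blood glucose values", with a literature footnote;
- samples are those at 15-minute intervals with a matching CGM value;
- data are free from protocol deviations, illustrated by examples rather than a closed list, and from flagged reference results.

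The SAP's Evaluable set, "participants with a minimum of three paired glucose readings", is close to the protocol's set but is only supportive.

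Two other SAP sections bear on this. Section 6.6.2 defines the primary endpoint on all paired measurements and does not refer to the restrictions in 6.2. Section 6.9 brings in samples taken more often than every 15 minutes, but only for the glucose-range strata.

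**The concern.** The study has no hypothesis test, so the MARD estimate and the data behind it are the effectiveness result. Under protocol 11.3 or SAP 6.6.2, an analyst would use every pair. Under SAP 6.2, an analyst would use a smaller set, possibly with altered reference values. Both would be following an approved document.

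The restrictions are not neutral across glucose levels. Protocol 4.3.9.2 calls for 5-minute draws only at or below 70 mg/dL or at or above 300 mg/dL, so a 15-minute rule removes pairs only from those ranges. The word describing equilibration adds a separate problem. If it means that YSI values are converted, both the numerator and the denominator of every pair's error change. The protocol also allows the Day 90 analysis to support a regulatory submission, so the headline set should be settled before that analysis.

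**Working it through.** **Reproducing the plan's pair count.** The inputs are protocol 4.3 (13 values at or below 70 mg/dL, or 16 at or above 300 mg/dL, at 5-minute spacing) and the table in 11.1.4 (160 inserted, challenge types split equally).

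- An 8-hour visit has 8 x 4 + 1 = 33 quarter-hour slots.
- Hypoglycemia visit: 33 - 5 + 13 = 41 pairs. Hyperglycemia visit: 33 - 6 + 16 = 43. Mean 42 (6.5 low, 27.5 middle, 8 high).
- Day 180 (10 hours): 41 slots, mean 41 + 9 = 50 pairs.
- Subject-visits before Day 180: 160 + 80 + 80 + 160 + 160 + 160 + 155 + 140 + 130 = 1,225.
- All pairs: 1,225 x 42 + 112 x 50 = 57,050. With 120 subjects at Day 180 the total is 57,450. Both match the table.

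**Applying the 15-minute grid, with 112 at Day 180.** The total is 1,225 x 33 + 112 x 41 = 45,017, a loss of 12,033 (21.1%).

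| YSI range, mg/dL | All pairs | Share | 15-minute grid | Share |
|---|---|---|---|---|
| 40-70 | 1,337 x 6.5 = 8,691 | 15.2% | 1,337 x 2.5 = 3,343 | 7.4% |
| 71-299 | 37,664 | 66.0% | 37,664 | 83.7% |
| 300-400 | 1,337 x 8 = 10,696 | 18.7% | 1,337 x 3 = 4,011 | 8.9% |

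The share outside 71-299 mg/dL falls from 34.0% to 16.3%. With 120 at Day 180 the grid total is 45,345, again a 21.1% loss.

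**Sensitivity to the challenge assumption.** Protocol 4.3 keeps some subjects on free-range control. If 30% of 8-hour visits had no 5-minute sampling (assumed), the mean would be 33 + 0.7 x 9 = 39.3 pairs and the loss 6.3/39.3 = 16%.

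**Sensitivity to the reading of the rule.** If only samples drawn on the 15-minute schedule count, the set shrinks towards the 37,664 middle-range pairs, a loss of up to 34%. SAP 6.2 does not say which reading applies.

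**Effect on MARD.** From the change in shares alone:

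shift = -0.078 x (low MARD - middle MARD) - 0.098 x (high MARD - middle MARD)

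The documents give no range-specific MARD. If both extremes were 5 points worse than the middle (assumed), the shift is -0.39 - 0.49 = -0.88 points. If both were 5 points better, it is +0.88.

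**Equilibration.** No rule is given, so only an illustration is possible. Take a simulated unbiased sensor with normal relative error (SD 11.3%) and MARD 9.0%. Rescaling the reference by an assumed -5%, +2% or +5% gives 10.4%, 9.0% or 9.4%. If the sensor reads 3% high, MARD starts at 9.3% and becomes 11.8% at -5% or 8.7% at +5%.

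**Pooling (secondary).** SAP 6.6.2 writes its formula for each participant, whereas the protocol pools pairs. On the table's exit pattern, 40 early exits contribute 5 x 210 + 15 x 252 + 10 x 294 + 10 x 336 = 11,130 pairs and 120 completers contribute 120 x 386 = 46,320. With assumed MARDs of 14% and 9%, the pooled value is 9.97% and the per-participant mean 10.25%.

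**The case against.** The strongest reply is that the SAP has not abandoned the protocol's measure. SAP 6.6.2 still uses all pairs, SAP 6.9 plans an all-samples analysis by glucose range, and shell A.7.1 has an overall row with MARD and pair count. That stands in part. It rules out saying that the SAP's headline MARD is simply not the protocol's, or that an all-samples figure will go unreported. What remains is that 6.2 and 6.6.2 disagree within the SAP, and that the A.7.1 row is not identified as the protocol's MARD.

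Second, a 15-minute set may be the better choice. The 5-minute draws are triggered by glucose value, so using all pairs gives challenge periods extra weight. This is a fair argument, and it belongs in the protocol with closed rules. Parts of the SAP are not in the public text, so the absence of a stated reason is weak evidence.

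Third, the equilibration phrase may only describe the sampling, in which case no formula is missing. That is possible, so one cannot say the set is irreproducible on every reading. The text does not settle the matter.

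A reader might also infer that SAP 6.1.3, which analyses visits "according to the nominal visit entered in the Case Report Form (CRF) regardless of if it is out of window", contradicts the deviation examples in 6.2 ("hematocrit out of window, visit out of window"). It does not: 6.1.3 is a default that yields where another section specifies otherwise, as 6.2 does.

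Version lag is not an explanation. The SAP follows protocol Version 7, the Rev 08 log entry lists no change of analysis set, and Rev 09 is stated not to affect statistical methods.

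**Conclusion.** The conflict is real and should be fixed before analysis. SAP 6.2 disagrees with protocol 11.1.5, 11.1.6, 11.3.1 and 11.3.2.1 and with SAP 6.6.2 on which pairs make up the primary MARD, and the equilibration phrase has no operative rule.

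The 21% loss of pairs and the halving of the extreme-range share depend on the 11.1.4 table (160 inserted, a completed challenge at every visit) and on thinning to a quarter-hour grid. They exclude any loss from deviations, which cannot be sized.

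A reader might infer that the narrower set was chosen to flatter the device, or that it will. The documents do not support either: they give no range-specific accuracy, and the illustrated shifts go both ways. Type I error, power and sample size are untouched because the study is descriptive. The per-participant wording and the reference range (40-400 mg/dL in the synopsis and SAP 3.2.1, all values in protocol 11.3.2.1) are secondary.

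**What to change.** 1. Name one primary effectiveness set in both documents and make SAP 6.2 and 6.6.2 agree. Either option works:
   - the protocol's all-pairs set, removing only source-flagged invalid YSI results as a stated exception to 11.1.5; or
   - the 15-minute, deviation-free set, by protocol amendment that gives the reason, closes the deviation list and says which sample is kept where draws are 5 minutes apart.
2. Compute the primary MARD on measured, unadjusted YSI. If an equilibration adjustment is kept, state it in full and report it only as a labelled sensitivity analysis. If the phrase only describes the sampling, say so.
3. In either case, report the all-pairs, unadjusted, pooled MARD, labelled as the protocol's measure, beside the 15-minute deviation-free MARD, each with its pair count. SAP 6.9 and A.7.1 already produce much of this.
4. State in SAP 6.6.2 that MARD is pooled over pairs, and use one reference range in both documents.

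The cost is SAP wording (or a protocol amendment), a little more analysis and one labelled row. The headline MARD may move in either direction.

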6.3 Handling of Missing Data

All attempts will be made to limit the amount of missing data. Unless otherwise specified, no attempt will be made to impute missing data. If a data point is missing, that data point will not contribute to that portion of the analysis. The number of evaluable observations will be reported in analysis so that extent of missing data can be assessed.

6.4 Subject Disposition

The number of subjects in each analysis population at each stage of the study, from informed consent to the end of study, will be presented along with reason for any exclusions. Subject accountability will be summarized by visit. The number of subjects who are enrolled, eligible for follow-up, and number completing clinical follow-up will be summarized for each protocol-required visit. In addition, the number of subjects who complete the study or exit early will be summarized by reason.

6.5 Demographics and Baseline Characteristics

Descriptive statistics will be presented for all clinically relevant baseline demographic (for example: age, sex, ethnicity), medical history (body mass index, diabetes type, insulin therapy, history of hypoglycemia or diabetic ketoacidosis), and participant characteristics.

6.6 Analysis of Study Endpoints

6.6.1 Safety Endpoints

The primary safety endpoint is defined as the incidence rate of device-related or procedure-related (from insertion or removal of the Sensor) serious adverse events occurring up to 180 days after the insertion procedure. The assessment of seriousness and relatedness will be made by the Medical Monitor. An adverse event is classified as “related” if its relatedness is assessed to be “possibly related” or “related”.

The number (and percentages) of serious adverse events and participants affected for each type of adverse event will be tabulated. No hypothesis testing will be carried out.

Apart from serious adverse events, other safety endpoints include:

Statistical Analysis Plan		Page 16 of 28
Sponsor Senseonics, Incorporated	Study PROMISE Study: A Prospective, Multicenter Evaluation of Accuracy and Safety of an Implantable Continuous Glucose Sensor Lasting up to 180 Days	Version 3.0

- Incidence rates of device-related or procedure-related (from insertion or removal of the Sensor) adverse events that occurred at home or during clinic visits.
- Incidence rates of any adverse events, serious or not serious, that occurred at home or during clinic visits.
- Incidence rate of hospitalizations due to hypoglycemia, hyperglycemia or ketoacidosis that occurred at home.
- Incidence rate of self-reported episodes of hypoglycemia or hyperglycemia that occurred at home.

For each of the above endpoint, the number (and percentage) of events and participants affected, stratified by age, will be presented as a table. A list of patients affected with information on date of onset, severity, seriousness, relatedness, classification as anticipated or unanticipated, corrective actions and resolution status will be prepared.

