Investigation Objectives	
Safety Objective: To demonstrate safety of the Eversense® 180 CGM System through 180 days post-Sensor insertion or removal and follow-up by measuring the incidence of device-related and insertion/removal procedure-related serious adverse events during the investigation.
 
After completion of Visit 8 (day 90 accuracy visit), analysis may be performed for the corresponding endpoints and may serve as the basis of a regulatory submission. After completion of Visit 12, analysis will be performed for subsequent visits. There are no formal hypothesis tests so there are no type I error concerns.

Measures/Endpoints	
Effectiveness Measures: The effectiveness measure will be mean absolute relative difference (MARD) for paired Sensor and reference measurements through 180 days post-insertion for reference glucose values from 40-400 mg/dL. Effectiveness measures will be evaluated descriptively. Neither inferential analysis nor hypothesis testing will be performed.
 
Safety Endpoint: Incidence of device-related or sensor insertion/removal procedure-related serious adverse events through 180 days post-Sensor insertion or removal and follow-up.

Other Safety Endpoints	
 1. Incidence of all device-related or sensor insertion/removal procedure-related adverse events in the clinic and during home use. 2. Incidence of all adverse events in the clinic and during home use. 3. Incidence of hospitalizations due to hypoglycemia, hyperglycemia or ketoacidosis occurring during home use. 4. Incidence of reported hypoglycemic and hyperglycemic events occurring during home use.

ABBREVIATIONS

AE	Adverse Event
BG	Blood Glucose
BG Meter	Blood Glucose Meter (also known as SMBG Meter)
β-HOB	β-hydroxybutyrate or “ketones,” also abbreviated B-HOB
BMI	Body Mass Index
CD	Compact disc
CFR	Code of Federal Regulations
CGM	Continuous Glucose Monitoring
CRF	Case Report Form
CRO	Contract Research Organization
DCF	Data Clarification Form
DKA	Diabetic Ketoacidosis
eCRF	Electronic Case Report Form
EDC	Electronic Data Capture
EKG	Electrocardiogram (also commonly abbreviated as ECG)
FDA	Food and Drug Administration
GCP	Good Clinical Practice
HbA1c	Hemoglobin A1c or A1C
HCT	Hematocrit
HIV	Human Immunodeficiency Virus
HHD	Hand Held Device
ICH	International Conference on Harmonization
IRB	Institutional Review Board
ISO	International Organization for Standardization
MARD	Mean absolute relative difference

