2.2 SAFETY

The safety objective is to demonstrate safety of the Eversense® 180 CGM System through 180 days post-insertion by measuring the incidence of device-related or sensor insertion/removal procedure-related serious adverse events (SAEs) during the investigation.

After completion of Visit 8 (day 90 accuracy visit), analysis may be performed for the corresponding endpoints and may serve as the basis of a regulatory submission. After completion of Visit 12, analysis will be performed for subsequent visits. There are no formal hypothesis tests so there are no type I error concerns.

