11.2 SAFETY ENDPOINTS

The safety endpoint is the incidence of device-related or insertion/removal procedure-related serious adverse events (SAEs) in the clinic and during home use through 180 days post-insertion.

An Adverse Event is considered 'related' if the relatedness is categorized as 'possibly related', or 'related'. The assessment of seriousness and relatedness made by the Medical Monitor will be used for analysis. The numbers of SAEs and the percentage of patients with SAEs will be reported for each SAE type that is observed, identified as device-related, procedure-related or unrelated to the study (Table 3 in APPENDIX 1). The count and proportion of patients experiencing at least one device-related or procedure-related SAE will be presented. No inferential statistical analysis will be performed.

Other safety endpoints include:

- Incidence of insertion/removal procedure or device-related adverse events in the clinic and during home use.
- Incidence of all adverse events in the clinic and during home use.
- Incidence of hospitalizations due to hypoglycemia, hyperglycemia or ketoacidosis occurring during home use.

- Incidence of reported hypoglycemic and hyperglycemic events occurring during home use.

For each of the adverse event (AE or SAE) categories above, the numbers of AEs and the percentage of patients with AEs will be reported for each AE type that is observed and be stratified by the target age enrollment categories (Tables 4A-4E in APPENDIX 1). A listing (Table 5 in APPENDIX 1) will be prepared that identifies each patient with a reported AE or SAE, and relevant information including date of onset, severity level, seriousness, relatedness to the device or procedure, classification as anticipated or unanticipated, corrective action(s) taken, and resolution status (resolved or ongoing).

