Incidence of reported hypoglycemic and hyperglycemic events occurring during home use	2	2 (2.8%)

Table 4B. Other Safety Endpoint for Subjects between 18 and 20 Years Old (Sample Data)

Type of Incidence	Number of Incidents	Number (%) of Subjects with Incidents
Incidence of device-related or insertion/removal procedure-related serious adverse events over the operating life of the Sensor	0	0 (0.0%)
Incidence of insertion/removal procedure or device-related adverse events in the clinic and during home use	12	11 (15.5%)
Incidence of all adverse events in the clinic and during home use	35	24 (26.6%)
Incidence of hospitalizations due to hypoglycemia, hyperglycemia, or ketoacidosis occurring during home use	0	0 (0.0%)
Incidence of reported hypoglycemic and hyperglycemic events occurring during home use	2	2 (2.8%)

Table 4C. Safety Endpoint for Subjects between 21 and 44 Years Old (Sample Data)

Type of Incidence	Number of Incidents	Number (%) of Subjects with Incidents
Incidence of device-related or insertion/removal procedure-related serious adverse events over the operating life of the Sensor	0	0 (0.0%)
Incidence of insertion/removal procedure or device-related adverse events in the clinic and during home use	12	11 (15.5%)
Incidence of all adverse events in the clinic and during home use	35	24 (26.6%)

Incidence of hospitalizations due to hypoglycemia, hyperglycemia, or ketoacidosis occurring during home use	0	0 (0.0%)
Incidence of reported hypoglycemic and hyperglycemic events occurring during home use	2	2 (2.8%)

Table 4D. Safety Endpoint for Subjects between 45 and 65 Years Old (Sample Data)

Type of Incidence	Number of Incidents	Number (%) of Subjects with Incidents
Incidence of device-related or insertion/removal procedure-related serious adverse events over the operating life of the Sensor	0	0 (0.0%)
Incidence of insertion/removal procedure or device-related adverse events in the clinic and during home use	12	11 (15.5%)
Incidence of all adverse events in the clinic and during home use	35	24 (26.6%)
Incidence of hospitalizations due to hypoglycemia, hyperglycemia, or ketoacidosis occurring during home use	0	0 (0.0%)
Incidence of reported hypoglycemic and hyperglycemic events occurring during home use	2	2 (2.8%)

Table 4E. Safety Endpoint for Subjects over 65 Years Old (Sample Data)

Type of Incidence	Number of Incidents	Number (%) of Subjects with Incidents

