3.1.2 Safety

To demonstrate safety of the Eversense® 180 CGM System through 180 days post-insertion or removal and follow-up by measuring the incidence of device-related and Sensor insertion / removal procedure-related serious adverse events during the investigation.

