3.2.2 Main safety endpoint

Incidence of device-related or sensor insertion/removal procedure-related serious adverse events up to 180 days post-Sensor insertion or removal and follow-up.

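### The main safety endpoint counts removal-procedure SAEs, but SAP 6.6.1 and protocol 11.2 close it 180 days after insertion while the synopsis, SAP 3.1.2 and SAP 3.2.2 run it on to removal and follow-up

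*SAP*

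**What the plan says.** Two statements of the endpoint stop at Day 180. SAP 6.6.1, which defines the endpoint for analysis, takes device-related and insertion- or removal-related "serious adverse events occurring up to 180 days after the insertion procedure". Protocol 11.2 counts the same kinds of SAE "in the clinic and during home use through 180 days post-insertion".

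Other statements go further:

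- Protocol synopsis, safety endpoint: "serious adverse events through 180 days post-Sensor insertion or removal and follow-up" (the safety objective in the synopsis uses the same window).
- SAP 3.1.2: "through 180 days post-insertion or removal and follow-up by measuring the incidence".
- SAP 3.2.2: "up to 180 days post-Sensor insertion or removal and follow-up".

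Protocol 2.2 points both ways, since it names Day 180 and also the whole investigation: "through 180 days post-insertion by measuring the incidence of device-related or sensor insertion/removal procedure-related serious adverse events (SAEs) during the investigation". The sample safety tables in protocol Appendix 1 use yet another label, "serious adverse events over the operating life of the Sensor"; this is a minor inconsistency.

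All of these versions include SAEs related to removal. Protocol 11.2 also promises a headline figure without restating its window: "The count and proportion of patients experiencing at least one device-related or procedure-related SAE will be presented". No section ranks one definition above another.

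**The concern.** The endpoint names removal as one of the procedures whose serious complications it measures, yet removal is scheduled at about the time the narrow window closes. Protocol 8.3 anticipates poor healing after removal, infection, and difficulty in removal that may need surgery. If such an event met the SAE definition and began after Day 180, an analyst working from SAP 6.6.1 would leave it out of the main count, and one working from SAP 3.2.2 would include it. The endpoint is descriptive, so the count is itself the result. Two competent analysts could report different headline figures, and the narrower figure can never be the higher one.

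**Working it through.** **Inputs**

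- Day 0 is the insertion date (SAP 6.1.2).
- Visit 11 is Day 180 with a window of -3/+2 days (synopsis, protocol 3.3.3), given as Days 177-182 in SAP 4.3.
- Removal is at Visit 11 or up to 7 days later (synopsis, protocol 3.3.3, SAP 4.3), and no later than Day 189 (protocol 4.4).
- The Visit 12 site check is 7 to 17 days after removal (protocol 4.5, SAP 4.3).

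**Reproducing the stated limit.** Latest Visit 11 plus the longest delay is 182 + 7 = 189, which matches protocol 4.4.

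**Removal days against the cut-off**

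- Removal at Visit 11 itself: Days 177-182, or 182 - 177 + 1 = 6 days. Four (177-180) are inside the window and 2 (181-182) are outside.
- Removal at Visit 11 or within 7 days: Days 177-189, or 189 - 177 + 1 = 13 days. Four are inside and 9 (181-189) are outside.

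**Time left after a removal inside the window.** For removals on Days 177, 178, 179 and 180 the window stays open for 3, 2, 1 and 0 days after the removal day.

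**Visit 12 after on-schedule removal.** Earliest 177 + 7 = 184; latest 189 + 17 = 206. That is 184 - 180 = 4 to 206 - 180 = 26 days past the cut-off. There are 6 visit days x 8 removal delays (0-7) x 11 follow-up days (7-17) = 528 combinations, and none falls on or before Day 180.

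**Early removal.** The first possible day of the site check is by Day 180 if removal is by Day 180 - 7 = 173. The whole check window is inside if removal is by Day 180 - 17 = 163.

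**Two-sensor subjects.** Removals on Days 365-374 (protocol 4.4.1) put Visit 16 at 365 + 7 = 372 to 374 + 17 = 391.

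**A caution on the visit table.** The schedule table in protocol section 4 appears to give Visit 11 a window of ±7 days, but the extracted table is visibly damaged. Taken literally, the earliest Visit 12 would be 173 + 7 = Day 180, or 173 + 3 = Day 176 if Visit 12 were also ±7. I rely on the text statements, which agree with each other.

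**The case against.** **The events are not lost.** This stands, and it limits the harm. Protocol 9.3.1 collects AEs until each subject's participation ends. SAP 6.6.1 itself lists incidence endpoints for related AEs and for all AEs, serious or not, with no Day 180 limit, and a listing with onset date, seriousness and relatedness. SAP 6.8 tabulates SAEs. A late removal SAE would be visible and datable; what is unsettled is whether it belongs in the main count.

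**180 days may only label the study phase.** SAP 6.6.2 uses the same span for effectiveness although Visit 11 runs to Day 182, and SAP 6.1.3 analyses visits by nominal label. That is suggestive, but SAP 6.1.3 concerns visit-based assessments, not the onset date of an adverse event. It also would not settle whether post-removal follow-up is included.

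**A reader might infer that every post-removal check, or every removal SAE, falls outside the window.** The documents do not support that. Protocol 4.4 sets no earliest removal day, and sensors may come out early for a replacement alert (5.4), unresolved infection (7.3) or withdrawal (7.6.5). After such removals the check can fall before Day 180. SAEs with onset by Day 180, including on the day of removal, still count. Days 184-206 describe Visit 12 after an on-schedule first removal only.

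**A reader might also take 9 of 13 as the share of removals or SAEs affected.** It is a count of permitted calendar days. Removal at the Visit 11 session may be the usual case, and its nominal day, 180, is inside the window.

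**Conclusion.** The contradiction is real and sits inside the SAP itself as well as inside the protocol. SAP 6.6.1 and protocol 11.2, read literally, can omit two groups of events from the main count: SAEs from removals on Days 181-189, and SAEs that begin after Day 180 following removals on Days 177-180. Any omission can only lower the count.

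The size is limited. There is no hypothesis test, no data are missing, and the events appear in other planned outputs. The documents give neither a distribution of removal dates nor a removal-SAE rate, so the number of SAEs affected cannot be estimated. The conclusion assumes that the Day 180 limit is applied to onset date and that the Visit 11 window is Days 177-182. The wide wording is itself loose, since it names no closing visit, but any natural reading goes past Day 180. It should be settled before analysis because it concerns the main safety result and the repair is mostly wording.

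**What to change.** Use one window, by onset date, in SAP 3.1.2, 3.2.2 and 6.6.1, in the protocol synopsis, 2.2 and 11.2, and in the safety table shells: related SAEs with onset from insertion through completion of post-removal follow-up for the first sensor period, meaning Visit 12, or study exit if Visit 12 is not attended. The synopsis and SAP 3.2.2 need editing too, because neither names Visit 12. The removal schedule itself does not change.

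Two-sensor subjects need an explicit rule. Protocol 4.4.1 has a new sensor placed in the same arm at first removal, while the SAP is written to protocol Version 7 and ends participation at Visit 12.

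- Apply the onset window first. A related SAE with onset through Visit 12 counts in the main endpoint unless the Medical Monitor attributes it solely to the second insertion.
- Put SAEs attributed solely to the second insertion, and all related SAEs with onset after Visit 12, in one separate extension table. This includes SAEs from removing the secondary and second primary sensors around Day 365. State that the main endpoint excludes them.
- For a two-sensor subject who misses Visit 12 but continues, set an end date; the last day of the Visit 12 window (removal + 17 days) would serve.

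Cost: wording in six sections and the table shells, one extra table, and one added attribution (first removal or second insertion) by the Medical Monitor, who already assigns procedure relatedness (protocol 13.13). SAE reports already name the procedure (9.3), and the main analysis already waits for Visit 12 (2.2). The reported SAE rate may be slightly higher.
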